5.6.1 Dose Modification for Hematologic and Non-Hematologic Toxicities

Treatment with itacitinib and everolimus may be delayed up to 4 weeks (28 days) to allow for resolution of toxicity. Subjects may resume treatment if no medical condition or other circumstance exists that, in the opinion of the investigator, would make the subject unsuitable for further participation in the study. The treating investigator should contact the Sponsor Medical Director to discuss the case of any subject whose treatment has been delayed for more than 28 days before restarting treatment with itacitinib and everolimus.

Because subjects may enter the study with extensive pretreatment and/or severe bone marrow infiltration by the primary disease, dose interruption and reduction rules are provided as guidelines (see Table 3, Table 4, Table 5 and Table 6). Individual decisions regarding dose reduction following the DLT period should be made using clinical judgment, taking into account relatedness of the AE to the study drug and the subject's underlying condition. Adverse events that have a clear alternative explanation or transient (≤ 72 hours) abnormal laboratory values without associated clinically significant signs or symptoms may be exempt from dose-reduction rules.

Table 3: Guidelines for Interruption and Restarting Study Drugs due to AEs suspected to result from itacitinib or everolimus

ADVERSE EVENT		ACTION TAKEN			
CE	CHEMISTRY				
•	AST and/or ALT > 3.0 × ULN or > 3.0 of the baseline if baseline was abnormal	Step 1: Interrupt itacitinib and everolimus up to 28 days until the toxicity has resolved to \leq Grade 1 (unless approved otherwise by the medical director).			
		Step 2: Restart itacitinib and everolimus at same dose, if unrelated. If assessed as related to itacitinib, restart at next lower dose. If assessed as related to everolimus, restart at next lower dose. Monitor as clinically indicated.			
НЕ	HEMATOLOGY				
•	$ANC \le 1.0 \times 10^9/L$ unless due to underlying disease	Step 1: Interrupt itacitinib and everolimus up to 28 days until the toxicity has resolved to ≤ Grade 1 or pre-therapy baseline.			
•	Platelet count is $< 60 \times 10^9/L$ unless due to underlying disease	Step 2: Restart itacitinib and everolimus at same dose; monitor as clinically indicated.			
•	Grade 4 ANC (< 0.5 × 10 ⁹ /L)	Step 1: Interrupt itacitinib and everolimus up to 28 days until the toxicity has resolved to ≤ Grade 1.			
•	\geq Grade 3 ANC with an oral temperature of at least 38.5°C OR with \geq Grade 3 infection. Platelet count is $< 35 \times 10^9/L$	Step 2: Restart itacitinib and everolimus at same dose, if unrelated. If assessed as related to itacitinib, restart at next lower dose. If assessed as related to everolimus, restart at the next lower dose. Monitor as clinically indicated.			

Itacitinib + everolimus in HL
Version 11.0
Page 37 of 72

	ADVERSE EVENT	ACTION TAKEN
O	THER	
•	Any Grade 1 or Grade 2 toxicity	Continue study treatment and treat the toxicity; monitor as clinically indicated.
•	Any Grade 3 toxicity, if clinically significant and not	Step 1: Interrupt itacitinib and/or everolimus up to 28 days until the toxicity has resolved to ≤ Grade 1.
	manageable by supportive care	Step 2: Restart itacitinib and/or everolimus at same dose if unrelated. If assessed as related to itacitinib, restart at next lower dose. If assessed as related to everolimus, restart at the next lower dose. Monitor as clinically indicated.
•	Any recurrent Grade 3 toxicity after dose reductions	Discontinue study itacitinib and/or everolimus administration. Exceptions require approval of sponsor.
•	Any other Grade 4 toxicity	Discontinue itacitinib and/or everolimus administration. Exceptions require approval of sponsor.

Table 4: Guidelines for Interruption and Restarting Study Drugs due to AEs suspected to result from everolimus

ADVERSE EVENT	ACTION TAKEN
	Non-infectious Pneumonitis ¹
Grade 1	No specific therapy is required Administer 100% of everolimus dose. However, depending on the clinical scenario,
	investigator may hold everolimus during the work-up.
Grade 2	Symptomatic only. Prescribe corticosteroids if cough is troublesome.
	Hold until recovery to \leq Grade 1. Subjects will be withdrawn from the study if they fail to recover to \leq Grade 1 within 28 days.
Grade 3	Prescribe corticosteroids if infective origin is ruled out. Taper as medically indicated.
	Hold treatment until recovery to ≤ Grade 1. May restart protocol treatment within 28 days at a reduced dose (by one level) if evidence of clinical benefit.
	Subjects will be withdrawn from the study if they fail to recover to ≤ Grade 1 within 28 days.
Grade 4	Prescribe corticosteroids if infective origin is ruled out. Taper as medically indicated.
	Discontinue treatment.
	Stomatitis ¹
Grade 1	Use conservative measures such as non-alcoholic mouth wash or salt water (0.9%) mouth wash several times a day until resolution
Grade 2	Withhold everolimus until improvement to Grade 0 or 1. Resume at same dose.
	If recurs at Grade 2, withhold until improvement to Grade 0 or 1. Resume at 50% of previous dose; change to every other day dosing if the reduced dose is lower than the lowest available strength.
Grade 3	Withhold everolimus until improvement to Grade 0 or 1. Resume at 50% of previous dose; change to every other day dosing if the reduced dose is lower than the lowest available strength.

Itacitinib + everolimus in HL
Version 11.0
Page 38 of 72

ADVERSE EVENT	ACTION TAKEN
Grade 4	Discontinue treatment.
	Hyperlipidemia
Grade 2	Treat with a 3-hydroxy-3-methyl-glutaryl (HMG)-CoA reductase inhibitor (e.g., atorvastatin, pravastatin) or appropriate lipid-lowering medication, in addition to diet. Subjects should be monitored clinically and through serum biochemistry for the development of rhabdomyolysis and other adverse events as required in the product label/data sheets for HMG-CoA reductase inhibitors.
Grade 3	Withhold everolimus until improvement to Grade 0, 1, or 2. Resume at 50% of previous dose
Grade 4	Discontinue treatment.

For additional details, refer to section 5.6.2

Table 5: Guidelines for Dose Reductions for Itacitinib

Current Dose	First Dose Reduction	Second Dose Reduction
300 mg QD	200 mg QD	Discontinue
400 mg QD	300 mg QD	200 mg QD
200 mg QD	Discontinue	Discontinue

Table 6: Guidelines for Dose Reductions for Everolimus

Current Dose	First Dose Reduction	Second Dose Reduction
5 mg QD	2.5 mg QD	Discontinue
2.5 mg QD	Discontinue	Discontinue

5.6.2 Adverse Events Described with Everolimus and Management

5.6.2.1 Non-infectious Pneumonitis

Non-infectious pneumonitis is a class effect of rapamycin derivatives. Cases of non-infectious pneumonitis (including interstitial lung disease) have also been described in subjects taking everolimus. Some of these have been severe and on rare occasions, a fatal outcome was observed.

A diagnosis of non-infectious pneumonitis should be considered in subjects presenting with non-specific respiratory signs and symptoms such as hypoxia, pleural effusion, cough or dyspnea, and in whom infectious, neoplastic and other non-medicinal causes have been excluded by means of appropriate investigations. Subjects should be advised to report promptly any new or worsening respiratory symptoms.

Subjects who develop radiological changes suggestive of non-infectious pneumonitis and have few or no symptoms may continue everolimus therapy without dose alteration. If symptoms are

Page 39 of 72

moderate (Grade 2), consideration should be given to interruption of therapy until symptoms improve. The use of corticosteroids may be indicated. Everolimus may be reintroduced at a reduced dose until recovery to Grade 1 or better.

For cases where symptoms of non-infectious pneumonitis are severe (Grade 3), everolimus therapy should be discontinued and the use of corticosteroids may be indicated until clinical symptoms resolve. Therapy with everolimus may be re-initiated at a reduced dose depending on the individual clinical circumstances.

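### For Grade 2 non-infectious pneumonitis, Table 4 says hold everolimus until Grade 1 or better, Section 5.6.2.1 only asks that a hold be considered, and nothing says which governs

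*Combined protocol and SAP*

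**What the plan says.** Two places in the current text deal with the same event at the same grade.

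- **Section 5.6.1, Table 4, Grade 2 pneumonitis row.** The instruction is "Hold until recovery to" Grade 1 or better, followed by "Subjects will be withdrawn from the study if they fail to recover to" that grade within 28 days. The row gives no dose for restarting. The Grade 1 row keeps everolimus at full dose, although the investigator may hold it during the work-up.
- **Section 5.6.2.1, moderate (Grade 2) symptoms.** Here "consideration should be given to interruption of therapy until symptoms improve". The paragraph ends: "Everolimus may be reintroduced at a reduced dose until recovery to Grade 1 or better".

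The two are linked. Below Table 4 the protocol says "For additional details, refer to section 5.6.2", and Section 10.1 also names Section 5.6.2 as a source for everolimus risks.

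Three other provisions bear on the reading:

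- Section 5.6.1 says of Tables 3 to 6 that the "dose interruption and reduction rules are provided as guidelines".
- Table 3 has a general row that continues study treatment for any Grade 1 or Grade 2 toxicity.
- Section 5.6 takes a subject off study permanently if a treatment-related toxicity arising after Cycle 1 has not resolved in 4 weeks.

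**The concern.** Table 4 gives an order with a grade threshold and a consequence. The section it cites for detail turns that order into something to think about, ends it at symptom improvement rather than at a grade, and leaves out the 28-day withdrawal. An investigator who looks up Section 5.6.2.1 could reasonably conclude that continuing everolimus during symptomatic Grade 2 pneumonitis is within the protocol. One who stops at Table 4 would conclude that it is not.

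What is at stake is patient safety. Section 5.6.2.1 itself says of pneumonitis cases on everolimus: "Some of these have been severe and on rare occasions, a fatal outcome was observed". Non-hematologic dose-limiting toxicity in Table 2 generally starts at Grade 3, so Grade 2 pneumonitis would not ordinarily count as one by its grade. The hold rule is therefore one of the main protections while the event is still moderate.

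**Working it through.** The point depends on no sample size, error rate or event rate, so there is nothing to compute. The check is a comparison of the two texts for Grade 2 pneumonitis.

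| Question | Table 4 (Section 5.6.1) | Section 5.6.2.1 |
|---|---|---|
| Is everolimus stopped? | Yes, stated as an instruction | To be considered |
| When does the hold end? | At Grade 1 or better | When symptoms improve; no grade attached |
| When may it restart? | After the hold ends | Literally, before Grade 1 is reached; probably meant as after |
| At what dose? | Not stated | A reduced dose |
| If there is no recovery in 28 days? | Withdrawal | Not stated |

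**Step 1: is the conflict only the word *until*?** No. Replace *until* with *after* in the last sentence of the Section 5.6.2.1 paragraph and the third row of the table agrees. The first row still differs: one text instructs a hold and the other asks that it be considered.

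**Step 2: does another rule settle it?**

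- The guideline status of Tables 3 to 6 allows departure from a default. It does not say which of two defaults applies.
- The 4-week limit in Section 5.6 applies after Cycle 1 whichever text is followed. It decides when a subject leaves the study, not whether everolimus is taken in the meantime.
- The general row in Table 3 points towards continuing treatment. Table 4 is the event-specific rule and would naturally take priority, but the protocol does not say so.
- No statement of precedence appears in Sections 5.6, 5.6.1 or 5.6.2.

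**Step 3: what is the reduced dose?** "Table 6: Guidelines for Dose Reductions for Everolimus" has a single step down, from 5 mg to 2.5 mg daily, and then discontinuation. For a subject at the protocol dose of 5 mg, the reduced restart dose in Section 5.6.2.1 is therefore 2.5 mg daily. A subject already at 2.5 mg has no lower level.

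**Step 4: can the consequence be sized?** Not from these documents. The nearest figure is in Section 1.4.2: one of 19 Hodgkin lymphoma patients in the earlier everolimus monotherapy study had Grade 4 pneumonitis. Section 1.1 gives the dose in that study as 10 mg. This shows that the event occurs in this population. It gives no Grade 2 rate at 5 mg, and no rate at which Grade 2 events worsen if dosing continues.

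**The case against.** The strongest case on the other side has four parts.

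**Permission to dose before recovery is a slip.** *Reintroduced* presupposes that the drug was stopped, and a reduced dose given only until recovery would leave no dose defined afterwards. This stands. A reader might infer that the protocol deliberately allows everolimus before the event has settled; the text does not support that as an intention.

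**The two end points nearly coincide.** Within Section 5.6.2.1 the category below moderate is few or no symptoms, where dosing continues unchanged, much like the Grade 1 row of Table 4. Symptom improvement can thus be read as return to Grade 1. This is a fair reading and narrows the gap, but it leaves open whether the hold is obligatory.

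**Table 4 is only a guideline.** Its title says so, and Section 5.6.1 leaves dose-reduction decisions after the dose-limiting toxicity period to clinical judgment. So it would be too strong to call Table 4 an absolute requirement. Even so, the row is worded as an instruction and attaches withdrawal to non-recovery, while the section it cites is worded as an option.

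**No harm is shown.** This also stands. One could count the tablets a subject might take during an unresolved episode, but nothing in the documents links such a quantity to an outcome. The sentence on severe and fatal cases concerns pneumonitis on everolimus in general, not Grade 2 cases continued on drug.

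**Conclusion.** The inconsistency is real and should be corrected. For one event at one grade, Table 4 instructs a hold to Grade 1 or better with withdrawal at 28 days. The section it refers to makes the hold a matter for consideration, and no rule of precedence resolves the difference. An investigator following Section 5.6.2.1 could keep giving everolimus during symptomatic Grade 2 pneumonitis.

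Its size is limited. The sample size, the complete-response criteria and the toxicity stopping boundaries do not depend on this rule, and no event rate is affected. A reader might infer that subjects could stay on everolimus with Grade 2 pneumonitis indefinitely. The 4-week limit in Section 5.6 rules that out after Cycle 1, so the conflict there concerns what happens within those 4 weeks.

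The conclusion assumes that Table 4, the firmer and more specific text, states what the sponsor intends. If the sponsor intended discretion at Grade 2, the texts would still need to be aligned, but in the other direction and with a reason given.

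**What to change.** Four wording changes:

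1. In Section 5.6.2.1, Grade 2, replace the sentence on considering interruption with an instruction to hold everolimus until the event is Grade 1 or better, and to withdraw the subject if that is not reached within 28 days.
2. In the same paragraph, change *until* recovery to *after* recovery.
3. Add the Grade 2 restart dose to Table 4 so that it matches Section 5.6.2.1: everolimus may be reintroduced at the reduced dose, which is 2.5 mg daily under Table 6. Without this, the governing text would lack a restart dose.
4. State that, for the events it lists, Table 4 governs over Section 5.6.2.1 and over the general Table 3 row that continues treatment for Grade 1 and Grade 2 toxicity. This also settles the smaller difference at Grade 3, where Table 4 speaks of holding and Section 5.6.2.1 of discontinuing with possible re-initiation.

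The changes touch protocol text only; the design and analyses stay as they are. They cost some investigator discretion at Grade 2. They also have one treatment consequence that the sponsor should confirm: a subject already at 2.5 mg daily has no lower everolimus level in Table 6, so a Grade 2 event at that dose would end everolimus. The amended text should say so.

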5.6.2.2 Hyperlipidemia and Management

Everolimus has been described to cause hyperlipidemia in some subjects. Treatment of hyperlipidemia should take into account the pre-treatment status and dietary habits. Blood tests to monitor hyperlipidemia must be taken in the fasting state. Grade 2 hypercholesterolemia (> 300 mg/dL) or Grade 2 hypertriglyceridemia (> 300 mg/dL) should be treated with a 3-hydroxy-3-methyl-glutaryl (HMG)-CoA reductase inhibitor (e.g., atorvastatin, pravastatin) or appropriate lipid-lowering medication, in addition to diet. Subjects should be monitored clinically and through serum biochemistry for the development of rhabdomyolysis and other adverse events as required in the product label/data sheets for HMG-CoA reductase inhibitors.

Note: Concomitant therapy with fibrates and an HMG-CoA reductase inhibitor is associated with an increased risk of a rare but serious skeletal muscle toxicity manifested by rhabdomyolysis, markedly elevated creatine kinase (CPK) levels and myoglobinuria, acute renal failure and sometimes death. The risk versus benefit of using this therapy should be determined for individual subjects based on their risk of cardiovascular complications of hyperlipidemia. See section 10 for additional information on risk.

5.6.2.3 Stomatitis and Management

Everolimus has been described to cause stomatitis/oral mucositis/mouth ulcers in some subjects. It should be treated using local supportive care.

Follow the paradigm below for treatment of stomatitis/oral mucositis/mouth ulcers:

- For mild toxicity (Grade 1), use conservative measures such as non-alcoholic mouth wash or salt water (0.9%) mouth wash several times a day until resolution.
- For more severe toxicity (Grade 2 in which case subjects have pain but are able to maintain adequate oral alimentation, or Grade 3 in which case subjects cannot maintain adequate oral alimentation), the suggested treatments are topical analysesic mouth treatments (i.e., local anesthetics such as benzocaine, butyl aminobenzoate, tetracaine hydrochloride, menthol, or phenol) with or without topical corticosteroids, such as triamcinolone oral paste 0.1% (Kenalog in Orabase®).
- Agents containing hydrogen peroxide, iodine, and thyme derivatives may tend to worsen mouth ulcers. It is preferable to avoid these agents.
- Antifungal agents must be avoided unless a fungal infection is diagnosed. In particular, systemic imidazole antifungal agents (ketoconazole, fluconazole, itraconazole, etc.) should be avoided in all subjects due to their strong inhibition of everolimus metabolism,

Itacitinib + everolimus in HL
Version 11.0
Page 40 of 72

thereby leading to higher exposures. Therefore, topical antifungal agents are preferred if an infection is diagnosed.

6 STUDY EVALUATIONS AND PROCEDURES

6.1 Screening

The screening period is the interval between the signing of the ICF and the day that the subject is enrolled in the study (Day 1). Informed consent must be obtained before performing any study-specific procedures, but imaging from standard of care prior to screening will be acceptable for baseline tumor measurement. A subject who fails screening may repeat the screening process 1 time if the investigator believes there has been a change in eligibility status (e.g., following recovery from an infection). Any screening studies done outside of this site's standard of care to obtain everolimus (ie any additional imaging or blood work) will be delayed until after everolimus was secured from insurance. Assessments that are required to demonstrate eligibility may be performed over the course of 1 or more days during this phase:

- Review and signing of the Informed Consent Form
- Complete medical history, including prior and current medications, treatments, and anticancer therapies.
- Physical Exam and evaluation of ECOG PS (Appendix 13.3)
- Vital signs, including blood pressure, heart rate, oral temperature and weight
- Imaging with PET/CT scan or CT scan or MRI scan to obtain baseline tumor measurements (within 8 weeks prior to initiating study treatment)
- Complete blood count with WBC differential, serum chemistry panel including sodium, potassium, chloride, CO₂, calcium, serum creatinine, BUN, total bilirubin, alkaline phosphatase, AST, ALT, albumin, uric acid, LDH, and erythrocyte sedimentation rate
- Viral screening tests to include testing for Hepatitis B (hepatitis B core antibody, hepatitis B surface antigen, hepatitis B surface antibody), Hepatitis C (hepatitis C antibody), HIV (HIV 1 and 2 antibody or viral load)
- Fasting lipid profile (triglycerides, total cholesterol, HDL and LDL)
- For women of childbearing potential, a serum pregnancy test must be performed within 72 hours prior to initiating treatment with itacitinib and everolimus unless the subject was undergoing egg harvesting (including hCG injections which may cause in elevated hCG levels) within 3 weeks prior to starting therapy; for those subjects, written statement from the treating fertility specialist is required to document that subject is not pregnant.

Page 41 of 72

6.2 Concomitant Medications

Prior and concomitant medications and procedures will be reviewed to determine study eligibility.

Both itacitinib and everolimus are metabolized by CYP 3A4. Subjects will be instructed not to take any additional excluded medications (including over-the-counter products; see Appendix 13.2) during the course of the study without prior consultation with the investigator. At each visit, the investigator will ask the subject about any new medications he/she is or has taken after the start of the study drug.

All Concomitant medications/Significant non-drug therapies taken \leq 30 days prior to start and after start of study drug, including physical therapy and blood transfusions, should be recorded.

The following conditions apply during the entire duration of the study:

- No other investigational therapy should be given to subjects.
- No anticancer agents other than the study medication should be given to subjects. If such agents are required for a subject then the subject must be withdrawn from the study.
- Oral contraceptives in preclinical and clinical data have shown everolimus to have CYP3A4 inhibitory activity rather than induction activity, induction of metabolism of contraceptive hormones by everolimus is unlikely. Consequently, administration of everolimus should not reduce the efficacy of oral contraceptives.
- No chronic treatment with systemic steroids (at a dose equivalent of greater than 20 mg prednisone per day) or other immunosuppressive agents. Topical or inhaled corticosteroids are allowed.
- The use of live vaccines and close contact with those who have received live vaccines should be avoided during the study treatment. Examples of live vaccines include intranasal influenza, measles, mumps, rubella, oral polio, BCG, yellow fever, some varicella and TY21a typhoid vaccines.
- Oral anticoagulants such as warfarin are CYP2C9 substrates and, as such, no interaction
 with everolimus/itacitinib is expected. However, drug-drug interaction studies between
 macrolide antibiotics and warfarin have produced mixed outcomes and the disparity in
 these findings has led to the conclusion that multiple factors may alter the clearance of
 warfarin. The co-administration of everolimus/itacitinib and oral anticoagulants is
 possible but should be subject to verification of coagulation (INR) once steady state is
 reached.
- All subjects will be treated prophylactically with an antiviral agent (e.g., acyclovir) to prevent varicella re-activation or other viral infections

Inhibitors of CYP3A4 and/or P-gp

Co-administration with strong inhibitors of CYP3A4 (e.g., ketoconazole, itraconazole, ritonavir) or P-glycoprotein (P-gp) should be avoided. See Appendix 13.2 for detailed list of medications.

Itacitinib + everolimus in HL

Version 11.0

Page 42 of 72

Co-administration with moderate CYP3A4 inhibitors (e.g., erythromycin, fluconazole) or P-gp inhibitors should be used with caution. If subject requires co-administration of moderate CYP3A4 inhibitors or P-gp inhibitors, reduce the dose of everolimus to half the currently used dose. If the inhibitor is discontinued the everolimus dose should be returned to the dose used prior to initiation of the moderate CYP3A4/P-gp inhibitor.

Seville orange, star fruit, grapefruit and their juices affect P450 and P-gp activity. Concomitant use should be avoided.

See Table 7 for a summary of actions to be taken when the use of a CYP3A4/P-gp inhibitor is required.

Table 7: Recommended Dosage Modifications for Concurrent Use of a P-gp substrate or CYP3A4 Inhibitor

Type of CYP3A4 inhibitor or P-gp substrate	ACTION TAKEN
Strong Inhibitor	For temporary use – discontinue both agents (everolimus and itacitinib) until completion of inhibitor therapy. For extended use (> 28 days) – discontinue from study.
Moderate Inhibitors	Reduce treatment of both agents (everolimus and itacitinib) to 50% during treatment with moderate inhibitors.
Weak Inhibitors	Use caution. No treatment adjustments required.

Note: See appendix 13.2 for a list of CYP3A4 inhibitors and P-gp substrates

Inducers of CYP3A4 and/or P-gp

Avoid the use of strong CYP3A4 inducers. If subject requires co-administration of strong CYP3A4 inducers (i.e., phenytoin, carbamazepine, rifampin, rifabutin, phenobarbital, St. John's wort), he or she should be removed from study. See Appendix 13.2 for detailed list of medications.

See Table 8 for a summary of actions to be taken when the use of a CYP3A4 inducer or P-gp substrate is required.

Table 8: Recommended Dosage Modifications for Concurrent Use of a P-gp substrate or CYP3A4 Inducer

Type of P-gp substrate or CYP3A4 Inducer	ACTION TAKEN
Strong Inducer	For temporary use - Use caution. No treatment adjustments required. For extended use (> 28 days) – discontinue from study.
Moderate Inducer	Use caution. No treatment adjustments required.
Weak Inducer	Use caution. No treatment adjustments required.

Note: See appendix 13.2 for a list of P-gp substrate or CYP3A4 Inducer

Itacitinib + everolimus in HL
Version 11.0
Page 43 of 72

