4.2 Exclusion Criteria

- 1. Unable to sign informed consent form.
- 2. Pregnant or breast-feeding females (lactating females must agree not to breast feed while taking the investigational agents).
- 3. Any condition, including the presence of laboratory abnormalities, which places the subject at unacceptable risk if he/she were to participate in the study or confounds the ability to interpret data from the study. For Example:
 - symptomatic congestive heart failure of New York Heart Association Class III or IV (Appendix 13.5)
 - unstable angina pectoris, symptomatic congestive heart failure, myocardial infarction within 6 months of start of study drug, serious uncontrolled cardiac arrhythmia or any other clinically significant cardiac disease
 - severely impaired lung function with O₂ saturation that is 88% or less at rest on room air
 - active (acute or chronic) or uncontrolled severe infections
 - condition requiring ongoing use of medications that are considered STRONG or MODERATE CYP3A4 inhibitors or inducers and P-gp substrates at study screening. However, those who require weak inhibitors/inducers can be enroll at discretion of the PI. See Appendix 13.2 for a list of excluded and cautionary concomitant medications.
 - liver disease such as cirrhosis or severe hepatic impairment (Child-Pugh class C).
- 4. Has a history (within the past 12 months) of (non-infectious) pneumonitis requiring systemic steroids, or active pneumonitis.
- 5. Bilirubin < 3 × ULN in the presence of liver metastases or presence of documented Gilbert's syndrome (unconjugated hyperbilirubinemia)
- 6. Concurrent use of other anti-cancer agents or therapies during study treatment.
- 7. Use of any other experimental drug or therapy within 28 days of initiating treatment with the investigational agents.
- 8. Known seropositive for or active viral infection with human immunodeficiency virus (HIV), hepatitis C (HCV), or hepatitis B virus (HBV); patients who are seropositive because of hepatitis B virus vaccine are eligible.
- 9. Previous use of JAK1 inhibitor (itacitinib), or history of progression on everolimus.

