5.1.3 Receipt

Itacitinib will be provided to the study team as 100 mg tablets. All Incyte investigational product labels will be in the local language and will state "Caution: New Drug--Limited by Federal (or United States) law to investigational use."

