13.2 Concomitant Medications/Products not to be taken

Examples of clinically relevant drug interaction: substrates, inducers and inhibitors of isoenzyme CYP3A4 and or P-gp (Note this is not an exhaustive list):

Excluded

Grapefruit, grapefruit products, Seville oranges (including marmalade containing Seville oranges), or starfruit

Strong CYP3A inhibitors:

boceprevir, clarithromycin, conivaptan, indinavir, itraconazole, ketoconazole, mibefradil, lopinavir/ritonavir, nefazodone, nelfinavir, ritonavir, posaconazole, saquinavir, telaprevir, telithromycin, voriconazole

Moderate CYP3A inhibitors:

amprenavir, aprepitant, atazanavir, ciprofloxacin, crizotinib, darunavir/ritonavir, diltiazem, erythromycin, fluconazole, fosamprenavir, imatinib, verapamil

Strong CYP3A inducers:

avasimibe, carbamazepine, phenobarbital, phenytoin, rifampin, St. John's wort

Moderate CYP3A inducers:

bosentan, efavirenz, etravirine, modafinil, nafcillin

Cautionary

Weak CYP3A inhibitors:

alprazolam, amiodarone, amlodipine, atorvastatin, bicalutamide, cilostazol, cimetidine, cyclosporine, fluoxetine, fluoxamine, ginkgo, goldenseal, isoniazid, nilotinib, oral contraceptives, pazopanib, ranitidine, ranolazine, tipranavir/ritonavir, ticagrelor, zileuton

Weak CYP3A inducers:

amprenavir, aprepitant, armodafinil, clobazamechinacea, pioglitazone, prednisone, rufinamide, vemurafenib

P-gp Inhibitor:

amiodarone, azithromycin, captopril, carvedilol, dronedarone, felodipine, quercetin, ronalzine, ticagrelor

Please note:

- strong inhibitor implies that it can cause ≥5-fold increase in AUC or ≥80% decrease in clearance of sensitive CYP substrates
- moderate inhibitor implies that it can cause 2 to 5-fold increase in AUC values or 50-80% decrease in clearance of sensitive CYP substrates (the distinction is not always categorical as interaction can vary according to conditions).

Itacitinib + everolimus in HL
Version 11.0
Page 69 of 72

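### For moderate CYP3A4 inhibitors the Section 6.2 text halves everolimus only, Table 7 halves both drugs, and half of the 300 mg itacitinib starting dose is 1.5 of the supplied tablets

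*Combined protocol and SAP*

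**What the plan says.** Section 6.2 (Concomitant Medications) treats moderate inhibitors twice. The running text allows them with caution and continues: "If subject requires co-administration of moderate CYP3A4 inhibitors or P-gp inhibitors, reduce the dose of everolimus to half the currently used dose". Once the inhibitor stops, everolimus goes back to its previous dose. Neither step mentions itacitinib. The text then points to Table 7 for a summary of the actions, and the row for moderate inhibitors reads: "Reduce treatment of both agents (everolimus and itacitinib) to 50% during treatment with moderate inhibitors".

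Three other places bear on whether such a medicine may be taken at all:
- Appendix 13.2, titled "Concomitant Medications/Products not to be taken", puts "Moderate CYP3A inhibitors" under its Excluded heading.
- Section 6.2 carries that list into the treatment period: "Subjects will be instructed not to take any additional excluded medications (including over-the-counter products; see Appendix 13.2) during the course of the study", unless the investigator has been consulted first.
- Exclusion criterion 3 in Section 4.2 names, as one example, a "condition requiring ongoing use of medications that are considered STRONG or MODERATE CYP3A4 inhibitors or inducers and P-gp substrates at study screening".

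On supply, Section 5.1.3 states: "Itacitinib will be provided to the study team as 100 mg tablets". The Study Summary and Section 1.2.1 describe these as sustained-release tablets. Section 5.2.3 names everolimus 5 mg tablets, with 2.5 mg as the only permitted substitute, and Section 5.2.6 requires everolimus tablets to be swallowed whole. Table 5 lists itacitinib at 400, 300 and 200 mg. Table 6 lists everolimus at 5 and 2.5 mg. In both tables the step below the lowest level is to discontinue.

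**The concern.** A table introduced as a summary should not add a reduction of the investigational drug that the text leaves out. As written, the protocol supports two different itacitinib doses for the same subject on the same day, and nothing says which statement governs.

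This affects subject safety and the record of exposure. Section 5.3 defines an overdose as any dose above the one the protocol specifies. If Table 7 governs, continuing full-dose itacitinib beside a moderate inhibitor would meet that definition. If the text governs, it would not. The documents cannot settle the classification.

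There is also a practical question. A 50% rule works only if half of each dose can be made from the tablets supplied, and it should say how it fits with the dose levels used elsewhere in the protocol. The moderate inhibitors in Appendix 13.2 include ciprofloxacin, fluconazole, diltiazem and verapamil, so the rule may well be needed during the trial.

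**Working it through.** The plan gives no figure to reproduce. The check has three parts.

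**1. Text against table (both in Section 6.2), moderate inhibitor needed**

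| | Section 6.2 text | Table 7 |
|---|---|---|
| Everolimus | 50% | 50% |
| Itacitinib | not mentioned, so 100% | 50% |
| After the inhibitor stops | everolimus restored | reduction limited to the inhibitor period |

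Ratio of itacitinib doses under the two readings: 100% / 50% = 2.

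**2. Can the halved dose be delivered, and is it a listed level?**

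Inputs: itacitinib levels of 200, 300 and 400 mg (Table 1, Section 1.6); itacitinib tablets of 100 mg (Section 5.1.3); everolimus levels of 5 and 2.5 mg (Table 6); everolimus tablets of 5 or 2.5 mg (Section 5.2.3). Formulas: halved dose = 0.5 × current dose; tablets needed = halved dose / tablet strength.

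| Current dose | Halved dose | Tablets needed | Listed in Table 5 or 6? |
|---|---|---|---|
| Itacitinib 400 mg | 200 mg | 200/100 = 2 | Yes |
| Itacitinib 300 mg (starting dose) | 150 mg | 150/100 = 1.5 | No |
| Itacitinib 200 mg | 100 mg | 100/100 = 1 | No; below the lowest level |
| Everolimus 5 mg | 2.5 mg | 2.5/2.5 = 1 | Yes |
| Everolimus 2.5 mg | 1.25 mg | 1.25/2.5 = 0.5 | No; below the lowest level |

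Three of the five halved doses have no match in the dose tables, and two of those three are not a whole number of tablets. The everolimus 2.5 mg row arises only for a subject already reduced from 5 mg. Table 4 has an every-other-day provision for doses below the lowest strength, but only for everolimus stomatitis. Table 7 has none.

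**3. Does the text-versus-table conflict change evaluability for dose-limiting toxicity?**

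Sections 3.2, 7.3 and 7.7 require the cohort-specific dose of both drugs on at least 75% of 28 days: 0.75 × 28 = 21 days, which leaves 28 − 21 = 7 days of tolerance. Everolimus is 5 mg in every cohort, and both readings halve it. Each day on a moderate inhibitor therefore misses the cohort-specific dose under either reading. The count of qualifying days is identical, so evaluability is too.

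**The case against.** The strongest reply is that the protocol is layered. Ongoing need for a moderate inhibitor bars entry, and that criterion applies at screening. On study the listed medicines are to be avoided unless the investigator is consulted. The Section 6.2 text and Table 7 then cover the case where use is unavoidable. Strong inhibitors are also listed as excluded, and Table 7 gives an action for them too. This largely answers a reader who might infer that Appendix 13.2 flatly contradicts Section 6.2. What remains is loose wording: the appendix title and its Excluded heading sit badly beside text that allows the same medicines with caution.

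Four further replies have force.
- Tables 5 and 6 belong to Section 5.6.1, on toxicity, and are described as guidelines. A reader might infer that they forbid itacitinib 100 mg or everolimus 1.25 mg. They do not say that they limit a temporary adjustment for an interaction, and 100 mg is one whole tablet.
- A reader might infer that 150 mg cannot be given at all. The swallow-whole instruction is written for everolimus; the itacitinib instructions in Section 5.1.6 say nothing about splitting.
- Appendix 13.2 is organised by interaction property, so one medicine can properly appear twice. Moving each medicine to a single category would lose information. The open question is only which heading governs for amprenavir and aprepitant, which appear under both Excluded (moderate inhibitors) and Cautionary (weak inducers).
- The trial has one centre, so differing practice between sites is not at issue.

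None of this touches the main conflict: the text and its summary table disagree on itacitinib.

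**Conclusion.** The point stands as an internal inconsistency. Within Section 6.2 the text and Table 7 give itacitinib doses that differ by a factor of two for the same subject. The Table 7 rule also produces 150 mg at the 300 mg starting dose, which is 1.5 tablets and not a Table 5 level. That this dose is undeliverable rests on the assumption that the sustained-release tablets may not be split, which the documents do not state. The rule is workable at itacitinib 400 mg and everolimus 5 mg. At itacitinib 200 mg and everolimus 2.5 mg the gap in Tables 5 and 6 is a missing cross-reference, with a deliverability question as well for everolimus 1.25 mg.

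A reader might infer that the conflict decides who counts in the Phase I tolerability review. It does not, because everolimus is halved under both readings. Taking a moderate inhibitor in Cycle 1 could still cost a subject's evaluability if it lasted more than 7 days without a dose-limiting toxicity, but that is true whichever instruction is followed, and such subjects may be replaced. No sample size, error rate or success criterion is affected.

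**What to change.** The sponsor should:
- reconcile the Section 6.2 text, Table 7 and Appendix 13.2 into one instruction per drug for moderate inhibitors, covering the period on the inhibitor and the period after it;
- make sure that the supplied tablet strengths can deliver the instruction at every protocol dose level, and state whether itacitinib tablets may be split;
- state how the instruction relates to the levels in Tables 5 and 6;
- state which heading in Appendix 13.2 governs when a medicine appears under both Excluded and Cautionary, as amprenavir and aprepitant do.

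Which dose or rule is right is a clinical decision for the sponsor, and none is proposed here. The cost is a wording amendment to the protocol; the design, sample size and analysis stay as they are.
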